## 5.5 Prophylactic and Standard of Care Migraine Medications

Patients on prophylactic migraine medication are permitted to remain on therapy if the dose has been stable for at least 2 months prior to the Baseline Visit, and the regimen should not change during the course of the study.

Patients may take their previously prescribed standard of care medications: aspirin, ibuprofen, acetaminophen up to 1000 mg/day for a maximum of 2 consecutive days at a time (this includes Excedrin Migraine), naprosyn (or any other type of non-steroidal anti-inflammatory (NSAID)), antiemetics (e.g. metoclopramide or promethazine) or muscle relaxants for standard of care during the course of the study (Observation Period and Long Term Treatment Phase).

Use of triptans by patients without a contraindication to their use is allowed during the Observation Phase but must be discontinued at the baseline visit. As described above, use of triptans is prohibited during the Long Term Treatment phase. With the exception of triptans and acetaminophen as described in this section, patients are allowed to take standard of care migraine treatment, if needed, during the course of the study.

If a patient takes a tablet of study drug and experiences a migraine later that day, after dosing with study drug for the day, the patient should take their standard of care migraine medication as described in this section of the protocol. Patients are not allowed to take more than one tablet of study medication per calendar day.

Use of standard of care medication during Observation Period and Long Term Treatment Phase, will be recorded by the patient on a paper diary and reported to the site.

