4.2.6 Subpopulations

The subgroups of interest for this study are the following:

- Intrinsic factors
 - Age: categorized as < 40, \geq 40, < 65, \geq 65
 - Sex: female, male
 - Sex and age: female < 40, female \geq 40, male < 40, male \geq 40
 - Race: white, black or African American, other including Asian, Asian
 - Ethnicity: Hispanic or Latino, not Hispanic or Latino
- Extrinsic disease-related factors
 - CV risk contraindicating triptans: yes, no (see Section 5.2.2)
 - Baseline body mass index (BMI; kg/m²): categorized as < 25, \geq 25 to < 30, \geq 30
 - Prophylactic migraine medication use on or after study drug start: yes, no (see Section 4.9)
- Extrinsic exposure factors
 - Time on rimegepant (weeks): categorized as quintiles for treated subjects (see Sections 4.8.1 and 5.2.3)

- Cumulative rimegepant exposure (tablets): categorized as quintiles for treated subjects (see Sections 4.8.1 and 5.2.3)
- Key factors
 - Average rimegepant exposure (tablets per 4 weeks): categorized as < 2, ≥ 2 to < 8, ≥ 8 to < 14, ≥ 14 for treated subjects (see Section 4.8.1)
 - Average rimegepant exposure (tablets per 4 weeks) for EOD+PRN treated subjects: categorized as < 14, ≥ 14 (see Section 4.8.1)
 - Treated subjects who took ≥ 14 tablets per 4 weeks for ≥ 12 weeks: categorized by enrollment group (see Section 4.8.1)
 - Treated subjects who took ≥ 20 tablets per 4 weeks for ≥ 4 weeks: categorized by enrollment group (see Section 4.8.1)
 - Treated subjects with near-daily dosing, defined as those in the (1) PRN dosing groups who took ≥ 14 tablets per 4 weeks for ≥ 12 weeks (see previous bullet), or (2) EOD+PRN dosing group: categorized by enrollment group.

Subgroup levels may be combined or redefined based on the availability of the data.

Subgroup tabulations will be by subgroup level and overall for treated subjects with non-missing subgroup level data. Refer to the BHV3000 Core SAP for rounding rules.

The triptan non-responder (yes, no) subgroup will be derived according to Section 5.2.1, included in the subgroup summary table (see Section 4.5), and excluded from subgroup tabulations by subgroup level and overall.

4.2.7 *Withdrawals, Dropout and Loss to Follow-Up*

Subjects who withdrew from the study were not replaced.

4.2.8 *Missing, Unused and Spurious Data*

Analyses will be based on observed data only.

4.3 *Planned Analyses*

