4.4 Study Population

4.4.1 Subject Disposition

Subject disposition will be summarized for screened subjects by enrollment group and overall as the number and percentage of subjects in the following categories:

- Screened (identified as subjects with non-missing informed consent date and enrollment group)
- Did not enroll in the LTT period (identified as screened subjects with missing IWRS enrollment date)
 - Did not enter the OP (identified as a subset with missing OP start date)
 - Reasons for discontinuation, including not reported*
 - Entered the OP (identified as a subset with non-missing OP start date)
 - Reasons for discontinuation, including not reported*
- Enrolled in the LTT period (identified as screened subjects with non-missing IWRS enrollment date)
 - Not treated (identified as enrolled subjects with missing study drug dose start date)
 - Reasons for discontinuation, including not reported*
 - Treated (identified as enrolled subjects with non-missing study drug dose start date)
 - Ongoing (identified as treated subjects with missing study drug last dose date)
 - Completed* (identified as treated subjects with non-missing study drug last dose date who completed)
 - Discontinued* (identified as treated subjects with non-missing study drug last dose date who discontinued)
 - Reason for discontinuation, including not reported*

The categories marked in with “*” will be based on the Study Exit Status CRF.

Subject disposition will be also be summarized for treated subjects by all subgroups of interest defined in Section 4.2.6.

Participation in previous Studies BHV3000-301/302/303 will be summarized by enrollment group and overall for the following populations: screened; enrolled; treated. The number and percentage of subjects in each previous study (total; 301; 302; 303) and treatment group (rimegepant, placebo) will be presented for each population. Note that subjects may participate in multiple studies and be in both treatment groups.

A by-subject listing of subject disposition information, including the reason for discontinuation and previous study participation, will be presented based on the Study Exit Status CRF for screened subjects.

A by-subject listing of eligibility with inclusion and exclusion criteria will be provided for all screened subjects, not just those who have non-missing criteria.

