Drug accountability is provided by the site on the Drug Accountability CRF.

A by-subject listing will present eDiary exposure (i.e., number of tablets taken) and drug accountability for treated subjects.

Another by-subject listing will present eDiary exposure (i.e., total number of tablets taken) in 4-week intervals during the LTT for treated subjects. This will also display cumulative rimegepant exposure from both sources (i.e., eDiary and drug accountability), and flag subjects with ≥ 10 cumulative tablet difference between the 2 sources.

Another by-subject listing will present batch numbers for treated subjects.

eDiary Exposure

eDiary exposure will be summarized descriptively for treated subjects by enrollment group and overall, and will include the following parameters:

- Time in the OP (weeks), defined as (OP end date – OP start date + 1)/7
- Time from enrollment to last contact (weeks), defined as (last contact date – IWRS enrollment date + 1)/7
- Time in the LTT period (weeks), derived as (LT_T end date – LT_T start date + 1)/7
- Time on rimegepant (weeks), derived as (study drug end dose date – study drug first dose date + 1)/7.*
- Cumulative rimegepant exposure (tablets), derived by summing number of tablets across records with complete dates for subjects who reported taking study medication during the treatment epoch in the eDiary.*
- Average rimegepant exposure (tablets per 4 weeks), derived as 4*cumulative rimegepant exposure/time in the LTT period.*
- Number and percentage of subjects in the average rimegepant exposure (tablets per 4 weeks) categories defined in Section 4.2.6, and also in the following categories:
 - ≥ 12.6 ($\geq 90\%$ compliant with EOD dosing)
 - ≥ 11.2 ($\geq 80\%$ compliant with EOD dosing)
- Number and percentage of subjects who took more than 1 tablet per day on any day. This could be from the same bottle or different bottles due to an unscheduled visit.
- Exposure over time, as defined by the number and percentage of subjects who took
 - ≥ 8 tablets per 4 weeks for 4, 8, 12, 16, 20, ≥ 24 , ≥ 12 , and ≥ 4 weeks. These categories correspond respectively to 1, 2, 3, 4, 5, ≥ 6 , and ≥ 3 4-week intervals that are not necessarily consecutive (see below)
 - ≥ 12 tablets per 4 weeks for 4, 8, 12, 16, 20, ≥ 24 , ≥ 12 , and ≥ 4 weeks
 - ≥ 13 tablets per 4 weeks for 4, 8, 12, 16, 20, ≥ 24 , ≥ 12 , and ≥ 4 weeks

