 - ≥ 14 tablets per 4 weeks for 4, 8, 12, 16, 20, ≥ 24 , ≥ 12 , and ≥ 4 weeks (the “ ≥ 12 weeks” category will support the subgroup “treated subjects who took ≥ 14 tablets per 4 weeks for ≥ 12 weeks” specified in Section 4.2.6)
 - ≥ 20 tablets per 4 weeks for 4, 8, 12, 16, 20, ≥ 24 , ≥ 12 , and ≥ 4 weeks
 - ≥ 25 tablets per 4 weeks for 4, 8, 12, 16, 20, ≥ 24 , ≥ 12 , and ≥ 4 weeks
- Total rimegepant exposure (tablets) summed across all subjects, derived by summing cumulative exposure across all subjects
- Total rimegepant exposure (patient-years), derived by summing (study drug end dose date – study drug first dose date + 1)/365.25 across all subjects.

This summary will also display quintiles (e.g., P20, P40, P60, P80, where “PX” denotes Xth percentile) for asterisked (“*”) continuous parameters to support the derivation of rimegepant exposure subgroups (see below). See Section 5.3 for derived dates.

eDiary exposure over time will assess the number of 4-week (28-day) intervals in which a subject exceeded select tablet counts in the LTT analysis period (see Section 5.4), where the number of 4-week intervals are not necessarily consecutive. For example, suppose a subject takes 20 tablets through 4 weeks (interval 1; LTT study days 1 to 28), 10 tablets after 4 weeks to 8 weeks (interval 2; LTT study days 29 to 56), 25 tablets after 8 weeks to 12 weeks (interval 3; LTT study days 57 to 84), and 15 tablets after 12 weeks to 16 weeks (interval 4; LTT study days 85 to 112). Thus, this subject is considered to have taken ≥ 14 tablets per 4 weeks for 12 weeks (i.e., intervals 1, 3 and 4), ≥ 20 tablets per 4 weeks for 8 weeks (i.e., intervals 1 and 3), and ≥ 25 tablets per 4 weeks for 4 weeks (i.e., interval 3). See Section 5.5 for the definition of LTT study days.

eDiary exposure will also be summarized by subgroup level and overall for treated subjects for all subgroups of interest described in Section 4.2.6.

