- TEAEs occurring in $\geq 2\%$ of subjects in any enrollment group after rounding. Percentages will be displayed rounded to integers, and AEs will be displayed in alphabetical order by SOC and PT.
- AEs occurring in $\geq 2\%$ of subjects in any enrollment group or subgroup level[^]
- AEs occurring in $\geq 5\%$ of subjects in any enrollment group by severity (primary safety endpoint, see Section 4.6.1)
- AEs occurring in $\geq 10\%$ of subjects in any enrollment group
- Exposure-adjusted AEs
- AEs related to study drug by severity*
- AEs related to study drug occurring in $\geq 2\%$ of subjects in any enrollment group or subgroup level[^]
- SAEs (primary safety endpoint, see Section 4.6.1)*
- Exposure-adjusted SAEs
- AEs leading to study drug discontinuation (primary safety endpoint, see Section 4.6.1)*
- Hepatic-related AEs by severity (secondary safety endpoint, see Section 4.6.2)[#]
- Hepatic-related SAEs[#]
- Hepatic-related AEs leading to study drug discontinuation (secondary safety endpoint, see Section 4.6.2)[#]
- Additional AEs of special interest: potential drug abuse[^]; CV; suicidality. Potential drug abuse AEs will be displayed in alphabetical order by severity and PT without SOC.

Endpoints marked with “*” will also be summarized by subgroup level and overall for all subgroups of interest specified in Section 4.2.6. Endpoints marked with “#” will also be summarized by subgroup level and overall only for extrinsic exposure factors (see Section 4.2.6). Endpoints marked with “^” will also be summarized by subgroup level and overall only for key extrinsic exposure factors (see Section 4.2.6).

Refer to the BHV3000 Core SAP for exposure-adjusted AEs. Calculations for on-treatment exposure-adjusted AEs will set reference start date to the study drug first dose date, reference end date to the study drug end dose date, and reference last date to the study drug last dose date + 7 days.

Follow-up AEs

Follow-up AEs will be summarized by SOC and PT for follow-up subjects by enrollment group and overall for the following endpoints:

- AEs by severity
- SAEs.

AEs in All Safety Analysis Periods Combined

AEs in all safety analysis periods combined (i.e., pre-treatment, on-treatment, and follow-up) will be summarized by SOC and PT for treated subjects by enrollment group and overall for the following endpoints:

- AEs leading to study drug discontinuation (primary safety endpoint, see Section 4.6.1)

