5.3 Derived Dates

Derived dates for defining analysis periods are defined as follows:

- OP start date/time: Earliest complete date during the screening epoch in the eDiary.
- OP end date/time: Latest complete date during the screening epoch in the eDiary.
- LTT start date/time: Earliest complete date during the treatment epoch in the eDiary.
- LTT end date/time: Latest complete date during the treatment epoch in the eDiary.
- Study drug first dose date/time: Earliest complete date where subjects indicated that they took medication during the treatment epoch in the eDiary.
- Study drug end dose date/time: Latest complete date where subjects indicated that they took medication during the treatment epoch in the eDiary.
- Study drug last dose date/time: Study drug end dose date derived only for subjects who have non-missing completion status on the Study Exit Status CRF. Thus, in an interim analysis, all post-treatment data will be included for a subject who is still on study. At the last database lock, the last dose date will be equal to the end dose date for treated subjects.
- EOT visit date: Maximum of the following: (1) LTT end date/time; (2) latest complete visit date excluding folder name “follow-up safety visit” on the Visit Date CRF. This is derived only for subjects who have non-missing completion status on the Study Exit Status CRF.

- Last contact date: (1) Complete death date, if it exists; (2) otherwise, the maximum complete date of the following: AE start/stop; ECG; eDiary; enrollment; informed consent; laboratory collection; non-study medication start/stop; physical measurement; procedure; rating scale; questionnaire; screening; study completion/discontinuation; vital sign; visit.

No imputations are performed on these derived dates. Complete dates are those with valid, non-missing day, month, and year.

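### The ≥ 14-tablets-for-≥ 12-weeks subgroup is defined by staying on drug, so its disposition and AE-discontinuation tables cannot show early stops and understate intolerance of frequent dosing

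*SAP*

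**What the plan says.** SAP 4.2.6 lists, among its key factors, "Treated subjects who took ≥ 14 tablets per 4 weeks for ≥ 12 weeks: categorized by enrollment group (see Section 4.8.1". SAP 4.8.1 explains the count: "eDiary exposure over time will assess the number of 4-week (28-day) intervals in which a subject exceeded select tablet counts in the LTT analysis period". It maps the duration categories to numbers of intervals: "These categories correspond respectively to 1, 2, 3, 4, 5, ≥ 6 , and ≥ 3 4-week intervals that are not necessarily consecutive". So ≥ 12 weeks means at least three qualifying intervals.

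The intervals run on a fixed calendar from LTT start. The SAP's worked example places the third one: "25 tablets after 8 weeks to 12 weeks (interval 3; LTT study days 57 to 84". SAP 5.3 defines day 1: "LTT start date/time: Earliest complete date during the treatment epoch in the eDiary". Protocol 5.5 caps intake: "Patients are not allowed to take more than one tablet of study medication per calendar day".

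The subgroup is then used for safety tables:
- SAP 4.4.1: "Subject disposition will be also be summarized for treated subjects by all subgroups of interest defined in Section 4.2.6".
- SAP 4.8.2 flags "AEs leading to study drug discontinuation (primary safety endpoint, see Section 4.6.1" for display in every 4.2.6 subgroup, together with SAEs and AEs by severity.
- SAP 4.6.3.1 and 4.8.3 do the same for LFT elevations and worst laboratory abnormalities.

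Under SAP 5.4 the on-treatment safety period opens at first dose, not on the day a subject meets the tablet criterion. The SAP gives no landmark, delayed entry or caveat for this subgroup, and SAP 2.3 makes no adjustment for intercurrent events.

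**The concern.** Membership depends on what happens later, while events are counted from the start. A subject who dosed daily and stopped for an adverse event in week 6 was a heavy user but cannot be a member. This is immortal time: everyone in the subgroup is known to have stayed on drug until the criterion was met.

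Tolerability is part of the primary objective, and AE discontinuation is one of the primary endpoints. The subgroup is shown by enrollment group, as the all-treated tables are, so the two invite side-by-side reading. A lower discontinuation percentage in sustained high users could be read as good tolerability of frequent dosing when part of the difference comes from the definition. The PRN part of the near-daily dosing subgroup uses the same criterion and inherits the problem.

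**Working it through.** **1. The interval rule reproduces the SAP's example.** Tablets of 20, 10, 25 and 15 in intervals 1–4 give:
- ≥ 14 tablets: three intervals, 12 weeks
- ≥ 20 tablets: two intervals, 8 weeks
- ≥ 25 tablets: one interval, 4 weeks

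These match SAP 4.8.1.

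**2. Earliest qualifying day.** Intervals 1 and 2 are LTT days 1–28 and 29–56, so a third cannot begin before day 57.
- One tablet per day: the 14th tablet of interval 3 falls on day 57 + 13 = 70.
- Every other day on odd days (57, 59, …): day 57 + 2 × 13 = 83. On even days: day 84.
- Cap broken: day 69 with one double dose in interval 3, day 63 at two tablets per day, and day 57 as the absolute floor set by the calendar.

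These are LTT days. Time on drug can be shorter: a first dose on LTT day 15 still allows 14 tablets in interval 1, and qualifying on day 70 then takes 70 − 15 + 1 = 56 days.

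**3. Share of AE stops excluded.** The documents give no AE-stop rate, so this is an illustration. Assume a constant hazard with risk q over T days. The share of stops before day d is [1 − (1 − q)^((d−1)/T)] / q.

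| Course | Assumed q | Before day 70 | Before day 83 |
|---|---|---|---|
| EOD+PRN, T = 84 | 1–5% | 82.2–82.5% | 97.6–97.7% |
| PRN, T = 364 | 1–10% | 19.0–19.8% | 22.6–23.5% |

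Example with q = 5%, T = 84: 1 − 0.95^(69/84) = 0.0413, and 0.0413/0.05 = 83%. For T = 364: 1 − 0.95^(69/364) = 0.0097, and 0.0097/0.05 = 19%.

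**4. What the table would then show for a true 5%**, as the risk left after the qualifying day is reached:
- EOD+PRN from day 70: 1 − 0.95^(15/84) = 0.9%. From day 83: 1 − 0.95^(2/84) = 0.1%.
- 52-week PRN from day 70: 1 − 0.95^(295/364) = 4.1%.

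**5. Which related subgroups share the feature.**
- Average exposure ≥ 14: SAP 4.8.1 uses 4 × tablets / weeks in LTT. Ten tablets over a ten-day LTT period give 4 × 10/(10/7) = 28, so an early stopper can be in it.
- Near-daily dosing: all EOD+PRN subjects enter whatever their duration. Only the PRN part carries the criterion.

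**The case against.** Much of the case on the other side stands.

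- **Other planned tables show the early stops.** For EOD+PRN, where the exclusion is largest, near-daily dosing takes the whole group, and the by-enrollment-group primary tables show its full discontinuation rate. The average-exposure ≥ 14 categories can hold heavy users who stopped early. These limit the harm, but they neither correct nor caveat the ≥ 12-week tables.
- **The effect is modest for most of the study.** About 1,800 of the 2,000 planned subjects are in the 52-week groups, where an assumed 5% shows as about 4%. A reader might infer that the subgroup will show almost no AE discontinuations across the study. The documents do not support that; the near-zero result applies only to EOD+PRN.
- **The condition is visible in the label, and the study is descriptive.** True, but the label does not tell a reader that events are counted from first dose in people selected for staying on drug. The descriptive percentages are the study's main result.
- **A footnote may already exist.** Table templates sit in a separate Mock TLF document, which is not available here. The SAP itself contains none.
- **Time-updated entry has its own gap.** Starting after one qualifying 28-day interval omits the first 28 days. For q = 5% over 84 days that is 1 − 0.95^(28/84) = 1.7%, or 34% of 12-week AE stops. It also asks a different question. It can therefore only supplement the other tables.

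Two further inferences go too far. Day 70 is not an absolute bar: SAP 4.8.1 counts subjects who took more than one tablet on a day, and the unconditional floor is day 57. Nor are all early events missing, since an early AE or LFT elevation in someone who later qualifies is counted. Only early stopping is structurally absent.

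**Conclusion.** The point holds for discontinuation. No one who stops before LTT day 70 with the cap kept (day 83 or 84 at every-other-day pace) can be in this subgroup, so its disposition and AE-discontinuation tables understate intolerance of frequent dosing. The exclusion follows from the definition and needs no assumed rate.

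Its size does rest on an assumption. Under a constant hazard it removes about 82–83% to 98% of 12-week AE stops in EOD+PRN (about 200 subjects) and about 19–20% of 52-week AE stops in the PRN groups. The PRN share would be larger if stops cluster early, or where the third qualifying interval comes later than interval 3.

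The EOD+PRN part of near-daily dosing is unaffected. A compliant EOD+PRN completer with an early end-of-treatment visit may also miss the third interval, but that is a separate, minor misclassification and assumes no as-needed tablet in that interval.

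This is a worthwhile, inexpensive change to the analysis. It does not affect the all-treated primary results.

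**What to change.** 1. Keep the ≥ 12-week definition for exposure counts and for descriptive AE and LFT tables.
2. Do not use its disposition and AE-discontinuation tables as evidence of tolerability. Footnote them as conditional on remaining on drug to at least about LTT day 70, and refer the reader to the average-exposure ≥ 14 tables and the full EOD+PRN group for discontinuations. Apply the same footnote to the PRN part of near-daily dosing.
3. Add one table of AE discontinuations, SAEs and LFT elevations in high users with time-updated entry: follow-up starts the day after a subject's first 28-day LTT interval with ≥ 14 tablets, and results are given as n and rate per patient-year.
4. State the limits of that table: it omits events in the first 28 days (about a third of 12-week AE stops under constant hazard) and describes risk after one heavy-use interval. It supplements the all-treated tables and does not replace them.

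The cost is SAP wording, footnotes, one entry-date variable and one table. Conduct and data collection do not change.
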